THE EFFECT OF HFNC ON MORTALITY AND  
ICU STAY TIME IN ACUTE RESPIRATORY  
FAILURE DUE TO COVID-19 PNEUMONIA

06.06.2020

Our study was planned retrospectively in 5 Covid Cohort intensive care units in our hospital to include the dates 15.03.2020 / 15.05.2020. The study started after getting approval from the local ethics committee of our hospital, ethics committee of the Ministry of Health .

All patient data, accepted for Covid cohort, between 15 March and 10 May 2020, were scanned. In our study, patients over the age of 18 years, who were admitted to the ICU unit due to acute respiratory failure due to Covid 19 pneumonia, whose diagnosis was confirmed by PCR test, and who received a conventional oxygen therapy (COT) with a reservoir mask were included. Data from patients who is with ongoing primary pulmonary pathology other than Covid -19 pneumonia, Glaskov coma score is below 12 or respiratory acidosis in the initial arterial blood gas were not included in the study.

The diagnosis of Covid-19 was made by PCR (Polymerase Chain Reaction) test, and the diagnosis of pneumonia was made by clinical and radiological findings. Acute respiratory failure is defined as espite the conventional oxygen treatment applied at 4 lt / min with a reservoir mask, the patient's ratio of PaO2 / FiO2 (ratio of partial oxygen pressure to inhaled oxygen fraction) is less than 300. HFNC could not be applied to all patients because the number of patients admitted to the ICU was above the unit and device capacity of HFNC. A selection criterion has not been established for this treatment and the order of application of the patients has been taken into consideration.

The study is divided into two groups. In the first group (group H), the data of patients undergoing HFNC treatment, and in group II (Group K), the data of patients who received COT

with a reservoir mask were included.

In HFNC support, the current air temperature is 31-37 degrees, the flow rate is 30-60 l / min, and the FiO2 value is targeted so that saturation is 93% and above. Initially, continuous treatment was applied intermittently after the PaO2 / FiO2 ratio exceeded 250 and clinical well-being occurred.

In patients in Group K, fingertip saturation was targeted as 93% and above, and a COT was applied with a reservoir mask with a flow rate of 6-15 l / min. The flow rate was calculated using the formula of FiO2 (%) = 21 + 4 \* (liters / min) in patients undergoing COT. Noninvasive mechanical ventilation was applied to patients who could not be provided with adequate clinical and laboratory well-being in both groups (PaO2 / FiO2 ratio below 150) and invasive mechanical ventilation if this was insufficient

Patient data were taken from our hospital's electronic information system and nurse observation records. Demographic data of patients in both groups, arterial blood gas values studied before treatment, PaO2 / FiO2 rates, orotracheal intubation times, intensive care hospitalization times, and forms of discharge from the intensive care unit (death or discharge) were recorded. Short-term mortality was defined as deaths during ICU hospitalization or after hospitalization for up to 28 days.

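### Entrants may already sit below the PaO2/FiO2 marker for escalation (150), and the plan neither says how they were handled nor stratifies or adjusts for the baseline ratio

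*Protocol*

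**What the plan says.** **Entry.** The protocol's definition of acute respiratory failure requires that, despite "conventional oxygen treatment applied at 4 lt / min with a reservoir mask", the "ratio of partial oxygen pressure to inhaled oxygen fraction) is less than 300". No lower limit is given. The exclusions do not supply one: they cover other primary lung disease and patients whose "coma score is below 12 or respiratory acidosis in the initial arterial blood gas were not included in the study".

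**Escalation.** In the description of treatment, "Noninvasive mechanical ventilation was applied to patients who could not be provided with adequate clinical and laboratory well-being in both groups". The only number attached is in brackets: "ratio below 150) and invasive mechanical ventilation if this was insufficient". No time point or minimum period on the assigned oxygen therapy is stated.

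**Treatment in the mask group (Group K).** After entry, "a COT was applied with a reservoir mask with a flow rate of 6-15 l / min". FiO2 is calculated as 21 + 4 × flow, a formula stated for "liters / min) in patients undergoing COT".

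**Group formation.** HFNC devices were too few for all patients. No selection criterion was set, and "the order of application of the patients has been taken into consideration".

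**Data and analysis.** The recorded items include pre-treatment blood gases, PaO2/FiO2, intubation times, ICU stay and the form of ICU discharge. Use and start of noninvasive ventilation are not listed. The SAP names the Mann-Whitney U and chi-square tests, with checks of normality. It has no stratification or adjustment.

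**The concern.** The entry range (below 300) contains the whole range that marks escalation (below 150). For a patient who enters below 150, the reader cannot tell whether the assigned oxygen therapy was given a trial first, or how long that trial lasted. What the HFNC-versus-mask contrast means for these patients is therefore unclear.

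They are also likely to be among the sickest entrants. The groups are not randomised, so nothing ensures that they hold equal shares of such patients, and the planned tests would not correct an imbalance. An unequal share would confound mortality and ICU stay, in either direction. An equal share would dilute a real effect if HFNC does less for these patients than for the rest.

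**Working it through.** The documents give no sample size, event rate, effect size or baseline distribution, so there is no design figure to reproduce. The first step uses document figures only. The others rest on assumed rates.

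**1. Where the two thresholds lie (protocol's formula).**
- Entry at 4 L/min: FiO2 = 21 + 4 × 4 = 37%.
- Ratio 300 at entry: 0.37 × 300 = 111 mmHg.
- Ratio 150 at entry: 0.37 × 150 = 55.5 mmHg.
- Group K on treatment at 6 L/min: FiO2 = 45%, and ratio 150 is 0.45 × 150 = 67.5 mmHg.
- Group K on treatment at 15 L/min: FiO2 = 81%, and ratio 150 is 0.81 × 150 = 121.5 mmHg.

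Every PaO2 below 111 mmHg qualifies for entry, and below 55.5 mmHg the number 150 is already undershot. The entry gas and the on-treatment gas are taken at different flows, so the two ratios do not test the same thing.

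**2. Imbalance (assumed rates).** Take mortality of 30% at 150 or above and 60% below 150, with no treatment effect. Let 30% of Group K and 20% of Group H (HFNC) be below 150.
- Group K: 0.70 × 0.30 + 0.30 × 0.60 = 0.39.
- Group H: 0.80 × 0.30 + 0.20 × 0.60 = 0.36.

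The 3-point difference is 0.10 × (0.60 − 0.30) and comes from case mix alone. Within each stratum the difference is zero.

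The opposite imbalance hides an effect. Assume HFNC lowers mortality from 30% to 21% at 150 or above and does nothing below. Let 20% of Group K and 30% of Group H be below 150.
- Group K: 0.80 × 0.30 + 0.20 × 0.60 = 0.36.
- Group H: 0.70 × 0.21 + 0.30 × 0.60 = 0.327.

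The crude difference is 3.3 points. With 30% below 150 in both groups it would be 6.3 (next table).

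**3. Dilution with equal shares (same assumed rates).** Group K = (1 − s) × 0.30 + s × 0.60; Group H = (1 − s) × 0.21 + s × 0.60, where s is the share below 150.

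| s | Group K | Group H | Difference (points) | Risk ratio |
|---|---|---|---|---|
| 0 | 0.300 | 0.210 | 9.0 | 0.70 |
| 10% | 0.330 | 0.249 | 8.1 | 0.75 |
| 30% | 0.390 | 0.327 | 6.3 | 0.84 |
| 50% | 0.450 | 0.405 | 4.5 | 0.90 |

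**4. How far dilution depends on the assumption.** If the risk ratio were also 0.70 below 150 (60% against 42%), then at s = 30% Group H is 0.70 × 0.21 + 0.30 × 0.42 = 0.273. The risk ratio is 0.273 / 0.39 = 0.70, so the ratio is not diluted. The imbalance in step 2 needs no such assumption. It needs only that mortality differs by baseline ratio and that the shares differ.

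**The case against.** The strongest reply is that the escalation rule describes failure to reach clinical and laboratory well-being, which reads as a response to treatment and not as a baseline trigger. That stands. An entrant below 150 meets the number, not necessarily the rule. A reader might infer that such patients went almost at once to noninvasive ventilation, but the documents do not say so. What they leave open is the timing.

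A reader might also infer that a Group K entrant below 150 had already failed that group's own treatment. The protocol's flows contradict this: the entry ratio is defined at 4 L/min, and Group K was treated at 6-15 L/min. Both groups received more support after the entry definition was met.

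It can further be said that a common rescue rule is no flaw, since mortality and ICU stay then compare two starting strategies with shared escalation. That also stands, and it is a reason to keep all eligible patients in the main result. Finally, imbalance in severity is ordinary confounding across the whole range of the ratio, not only at 150. That is true, and it supports adjusting for the ratio itself as an alternative to two strata. It does not excuse a plan that does neither.

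**Conclusion.** The concern holds in a limited form. Three things are established: the overlap of the entry and escalation ranges, the silence on timing and handling, and the lack of any stratification or adjustment in non-randomised groups. The direction and size of any bias are not known. The figures of 3 points for a 10-point imbalance, and risk ratios of 0.75 to 0.90 for shares of 10% to 50%, rest on assumed mortality. The dilution figures also rest on assuming no HFNC effect below 150.

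It is tempting to add that these patients dominate the deaths, but the documents give no event counts to support that. Even under the assumed rates they supply 0.06 / 0.330 = 18% of Group K deaths at a 10% share and 0.18 / 0.390 = 46% at 30%. They pass half only when s × 0.60 exceeds (1 − s) × 0.30, that is, above a one-third share. Nor do the documents justify moving the main conclusion to the subgroup at 150 to <300. That would drop the sickest patients on the strength of a rescue status that has not been shown.

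**What to change.** - **Reconcile** the protocol's entry definition with its escalation rule: state when the rule began to apply and how entrants below 150 were handled. This asks for a description of what was done; it takes no view on which threshold is right.
- **Keep all eligible patients** as the main population, and report the number with baseline PaO2/FiO2 below 150 in each group. State which gas and which flow the baseline ratio comes from.
- **Present mortality, ICU stay and intubation by baseline stratum** (<150, 150 to <300), with a group comparison stratified by these strata or adjusted for the baseline ratio. A Mantel-Haenszel analysis for the binary outcomes and a stratified rank test for ICU stay would serve.
- **Add a sensitivity analysis** restricted to 150 to <300.

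The split uses a pre-treatment value that the protocol already lists, so it involves no selection on later events and changes no care. The cost is a short addition to the SAP, a little more analysis and wider intervals within strata. Confounding by other factors, and by severity within strata, will remain.

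### The recorded baseline items name no comorbidity, general severity score, illness duration, pre-ICU drug treatment or arrival order, so the HFNC comparison may carry residual confounding of unknown size that adjustment for the listed items could not reveal or remove

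*Protocol*

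**What the plan says.** The Protocol describes the design as follows: "Our study was planned retrospectively in 5 Covid Cohort intensive care units in our hospital". It says some patients went without HFNC because "the number of patients admitted to the ICU was above the unit and device capacity of HFNC", and describes allocation in one sentence: "A selection criterion has not been established for this treatment and the order of application of the patients has been taken into consideration".

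Its paragraph on data sources states: "Patient data were taken from our hospital's electronic information system and nurse observation records". The recorded items are then "Demographic data of patients in both groups, arterial blood gas values studied before treatment", followed by "PaO 2 / FiO 2 rates, orotracheal intubation times, intensive care hospitalization times", and finally "forms of discharge from the intensive care unit (death or discharge) were recorded". Intubation times, ICU stay and discharge status arise after treatment starts. That leaves demographics, blood gases and PaO2/FiO2 to describe patients at baseline.

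The eligibility paragraph narrows the population somewhat. Patients with another ongoing primary lung disease are left out, and so are those whose "Glaskov coma score is below 12 or respiratory acidosis in the initial arterial blood gas were not included in the study".

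The SAP names chi-square and Mann-Whitney U tests, checks of normality, and a 0.05 significance level. It contains no regression, matching, weighting or covariate list.

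**The concern.** The title announces an effect of HFNC on mortality and ICU stay. Without randomisation, that reading needs the two groups to have similar prognosis, or the differences to be measured and adjusted for.

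The exclusions leave cardiac, renal, metabolic and malignant disease in the population, and none of these is named among the recorded items. Extra-pulmonary organ failure, time since symptom onset and drugs started before ICU are not named either. If such factors differ between the groups, the mortality difference absorbs the imbalance. Adding a model to the SAP would not cure this by itself, because a model can adjust only for what was extracted.

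The allocation statement offers some protection but cannot be tested as the plan stands. Neither admission date nor arrival order is listed, so nobody can check afterwards whether the order was kept. Baseline balance on comorbidity and severity, the natural indirect evidence, is not listed either.

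**Working it through.** **No figure to reproduce.** The documents give no sample size, event rate, effect size or power. Everything numerical below is an assumption, used to show what imbalance in one unrecorded factor would do.

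**Step 1: what the listed items cover.**

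| Domain | Named in the Protocol? |
|---|---|
| Demographics | Yes, not itemised |
| Gas exchange (blood gases, PaO2/FiO2) | Yes |
| Comorbidity | Not named |
| General severity or organ-failure score | Not named |
| Days since symptom onset | Not named |
| Drug treatment begun before ICU | Not named |
| Admission date, arrival order, device availability | Not named |

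**Step 2: bias from one unrecorded binary factor.** Suppose HFNC has no effect. Let the factor multiply mortality by RR, with prevalence pH in the HFNC group (Group H) and pK in the mask group (Group K). The spurious risk ratio, K versus H, is

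B = [1 + pK(RR − 1)] / [1 + pH(RR − 1)].

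Assume pH = 0.30 and mortality of 40% in Group H.

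- Equal prevalence (pK = 0.30), any RR: B = 1.00.
- RR = 1.5, pK = 0.40: B = 1.20/1.15 = 1.043, so 40% against 41.7%.
- RR = 2, pK = 0.50: B = 1.5/1.3 = 1.154, so 40% against 46.2%.
- RR = 2.5, pK = 0.50: B = 1.75/1.45 = 1.207, so 40% against 48.3%.

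**Step 3: false rejection by an unadjusted 5% test.** With n patients per group and mortalities mH and mK, take z = |mK − mH| / √{[mH(1 − mH) + mK(1 − mK)]/n}. The two-sided rejection probability is Φ(z − 1.96) + Φ(−z − 1.96). The SAP does not say whether its tests are two-sided, so that too is assumed.

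For RR = 2, pK = 0.50 and n = 100, the standard error is √[(0.240 + 0.2485)/100] = 0.0699, z = 0.0615/0.0699 = 0.88, and rejection is 14.2%.

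| Scenario | B | Rejection |
|---|---|---|
| No imbalance, any n | 1.00 | 5.0% |
| RR 1.5, 30% v 40%, n = 100 | 1.04 | 5.7% |
| RR 2, 30% v 50%, n = 50 | 1.15 | 9.5% |
| RR 2, 30% v 50%, n = 100 | 1.15 | 14.2% |
| RR 2, 30% v 50%, n = 150 | 1.15 | 19.0% |
| RR 2.5, 30% v 50%, n = 100 | 1.21 | 21.9% |

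Exchanging the two groups gives the same rejection rates with the bias against HFNC. The upper end is a chosen scenario and not a bound: a factor that triples mortality, at 20% v 50%, gives 2.0/1.4 = 1.43. ICU stay cannot be illustrated in the same way, because the documents say nothing about its distribution.

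**The case against.** The strongest reply is the allocation statement. If devices were given out in order of application, comorbidity and organ failure have no stated route into the choice of treatment. The bias factor could then be 1.00, and the more direct concern would be calendar time and device availability. That stands as a possibility. It does not settle the matter, because the plan describes no allocation log and lists nothing by which the order could be checked.

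Three further replies have weight.

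- Respiratory severity is recorded, and demographics would ordinarily include age, so part of patient risk could be adjusted for. However, PaO2/FiO2 describes gas exchange alone, and in the mask group its FiO2 comes from a flow formula. It cannot stand in for chronic disease or failure of other organs.
- The exclusions remove some imbalance in lung disease, consciousness and ventilatory failure. They also show that more clinical data were read than the recorded items name.
- The list is one sentence, and demographic data are not itemised. Comorbidity is therefore unnamed, which is not proof that it went uncollected.

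Finally, the SAP plans no adjustment at all, and that is the more immediate gap. It does not dispose of this point: a model added without wider extraction would leave these factors untouched.

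**Conclusion.** The point holds as a possibility of residual confounding, of unknown size and direction, that the planned data and tests could neither show nor remove. Under the stated assumptions the spurious mortality risk ratio runs from 1.00 to about 1.21, and false rejection at 100 per group from 5% to about 22%. The lower end is no problem at all and the upper end is material. The documents do not say where in that range the study lies.

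A reader might infer that even an adjusted comparison would certainly retain the main part of the confounding by patient risk. The documents do not support this. They record gas exchange, describe allocation by order under device limits, and give nothing to rank one source of confounding above another. Nor do they establish that the missing items are available: the data sources are named but their contents are not. The change is worth making because it is inexpensive and useful either way. Good balance would support the arrival-order account, and poor balance would show that adjustment is needed.

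**What to change.** 1. Itemise the baseline variables, including what demographic data means.
2. Where the records hold them, add main comorbidities (diabetes, hypertension, chronic heart and kidney disease, malignancy), a severity score or its components, days from symptom onset, drug treatment begun before ICU, and ICU admission date or arrival order with HFNC device availability. Use only values dated before HFNC or mask treatment began, so that nothing affected by treatment enters the adjustment.
3. Tabulate all of these by group with standardised differences, and use arrival order and device availability to check the allocation account.
4. Prespecify in the SAP an adjusted comparison of mortality and of ICU stay using these items with age, sex and baseline PaO2/FiO2. Limit the number of covariates to what the number of deaths supports.
5. Report a sensitivity analysis for unmeasured confounding, labelled as resting on assumptions and with zero imbalance included in its range.

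The cost is extra reading of records already in use, with no new patients or procedures. The downside is some missing values in the added items, so the SAP should also say how they will be handled. If an item proves unavailable, the report should say so and name it as a limitation.
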